PARTNERS HUMAN RESEARCH COMMITTEE DETAILED PROTOCOL

Version: March 8, 2017

Title: Pharmacologically improving the pharyngeal muscle activity during sleep: implications for the novel treatment of obstructive sleep apnea.

Principal Investigator: [name], PhD

I. BACKGROUND AND SIGNIFICANCE

Obstructive sleep apnea (OSA) is characterized by repetitive collapse or ‘obstruction’ of the pharyngeal airway during sleep. Over the last decade, and particularly in the last few years, research has shown that a number of pathogenic factors, or traits, contribute to the development of OSA (1-4). These include: 1) an anatomically small, collapsible upper airway; 2) an oversensitive respiratory control system leading to ventilatory overshoots and undershoots, i.e., instability; 3) a loss of pharyngeal muscle tone or responsiveness during sleep; and 4) a low respiratory arousal threshold, i.e., premature arousal to respiratory stimuli.

Despite our improved understanding of the pathogenesis of OSA, it has not led to improved therapy. Continuous positive airway pressure (CPAP) is still the only viable treatment for most patients, and it is usually effective because it mechanically splints the upper the airway open. The problem, however, is that many patients cannot use CPAP because they find it intolerable. This represents a significant health concern, as OSA is known to cause a number of adverse cardiovascular (5-12), neurocognitive (13), and daytime functioning (14) consequences.

One possible approach to finding alternative treatments for OSA is to continue searching for a single drug or agent that, like CPAP, has a large enough effect size to override the various causes of OSA. This approach has proven difficult, and while we hold out hope for such a drug, in the meantime we have adopted another (possibly equally effective) tactic, which is to target the relevant upstream mechanisms or individual traits with one or more drugs in an individual patient. The rationale for this approach is that non-CPAP therapies have tended to have small effect sizes and proven, by themselves, marginally effective at fully correcting OSA in many patients. Another reason stems from the manner in which most major medical disorders are treated. Rarely is a single drug used to treat, for example, congestive heart failure, hypertension, asthma, etc., unless the condition is mild. In our view, a similar approach should be taken for managing OSA.

Regardless of whether single or multidrug therapy is ultimately used, the search for alternative treatments has been lacking a very important ingredient – a drug to stimulate the pharyngeal muscles. While a host of oral devices and surgeries have been developed to address the anatomical predisposition to collapse, and our group has made significant headway in dealing with ventilatory control sensitivity (15, 16), drugs that activate the pharyngeal muscles are needed. Interestingly, new research in animals has improved our understanding of the state-dependent neurotransmitters involved in pharyngeal muscle activation during sleep. Importantly, the loss of noradrenergic activity is now thought to play the key role in the sleep-related hypotonia of pharyngeal muscles.

Chan and colleagues (17) showed in rats that the noradrenergic antagonist terazosin substantially reduced genioglossus (a major muscle of the upper airway) activity (EMG_{GG}) during wakefulness and produced REM-like atonia during NREM sleep, illustrating the importance of noradrenergic mechanisms. Other studies (18, 19) also support the notion that progressive withdrawal of noradrenergic tone, from wakefulness to NREM and REM sleep, is the major mechanism causing sleep-related pharyngeal hypotonia. While noradrenergic withdrawal is thought to be the main cause of pharyngeal hypotonia in NREM sleep, there are additional mechanisms that cause further reduction in REM sleep. Chan and colleagues (17) failed to reverse REM atonia with alpha-1 receptor agonists applied to the hypoglossal

PARTNERS HUMAN RESEARCH COMMITTEE

DETAILED PROTOCOL

Version: March 8, 2017

nucleus, suggesting that another, possibly inhibitory, mechanism is at work. Horner and colleagues have identified this inhibitory process as muscarinic by demonstrating restoration of EMG_{GG} activity during REM sleep with the muscarinic antagonist scopolamine (20, 21). More recently, these researchers found that the multiple state-dependent adrenergic, serotonergic and muscarinic systems produce suppression of EMG_{GG} activity during sleep via a convergent ionic mechanism: increased potassium conductance. Blockade of potassium channels has been shown in mice to be capable of reactivating the pharyngeal musculature throughout sleep (22).

However, due to the only recent identification of this process, there has not yet been an attempt to stimulate the pharyngeal muscles with noradrenergic drugs in sleeping humans. Now, more than ever, the stage has been set for stimulating the pharyngeal muscles across both NREM and REM sleep.

II. SPECIFIC AIMS

To determine the effect of noradrenergic, antimuscarinic and potassium channel blocker drugs on pharyngeal muscle activity during sleep. We hypothesize that existing drugs with these neurotransmitter profiles could (partially) restore pharyngeal muscle activity in humans during sleep.

Specifically, we will test this hypothesis by assessing;

The effect of the combination of atomoxetine (a norepinephrine reuptake inhibitor) plus fesoterodine (a newer, extended-release antimuscarinic drug) on OSA severity (DAW1033B2). Fesoterodine is an extended-release antimuscarinic with less reported side effects compared to oxybutynin. Fesoterodine could be a good candidate for a long-term therapy in subjects with OSA and the data collected in this pilot study will help to design a long-term clinical trial to test the efficacy of this association for the treatment of OSA.

1.

III. SUBJECT SELECTION

We will recruit a group of subjects with OSA. These subjects will be recruited from the community and be between 21-65 years old. The purpose of studying patients with OSA is to determine what effect this drugs will have on improving the patient's OSA severity.

- a) **Obstructive Sleep Apnea Patients (n= 15):** Patients with OSA will be recruited from our clinical sleep laboratory at Brigham and Women's Hospital, as well as from our existing database of OSA patients. These individuals will be otherwise healthy (except for well-controlled hypertension; defined as systolic blood pressure <140 mmHg and diastolic <90 mmHg) with no active medical problems and on no medication that could affect respiration or muscle control. All will be 21-65 years of age. Both men and women will have an apnea-hypopnea index (AHI) >15 events/hr during supine NREM sleep. These individuals will be recruited to encompass a large range of AHI's (from 10 to >60/hour).

Exclusion criteria:

- Any medical condition other than well controlled hypertension, GERD, hyperlipidemia.
- Any medication known to influence breathing, sleep/arousal or muscle physiology.
- Claustrophobia.
- Inability to sleep supine.
- Allergy to lidocaine, Oxymetazoline HCl, desipramine, atomoxetine/oxybutynin, dalfampridine, pseudoephedrine HCl, diphenhydramine.

PARTNERS HUMAN RESEARCH COMMITTEE DETAILED PROTOCOL

Version: March 8, 2017

- Benign prostatic hyperplasia or urinary retention, which can be exacerbated by antimuscarinics.
- Individuals with underlying cardiac disease, such as arrhythmias.
- Individuals taking psychiatric medications, such as Tricyclic antidepressants, or any of the studied medications for medical care.
- History of seizures
- History of moderate or severe renal impairment
- For women: Pregnancy.

Equal number of males and females will be recruited, recognizing that OSA is a more prevalent condition in men. We will consider all applicants regardless of sex, race, color, creed, or national origin.

IV. SUBJECT ENROLLMENT

Subjects will be recruited through email, telephone, newspaper, and or bulletin advertisements. Men and women with OSA will be recruited from a pool of patients being newly diagnosed with OSA and currently followed in our outpatient clinic or by advertisement in the sleep disorders clinic. Only patients who have stated in the initial clinical questionnaire that they are interested in hearing about research studies will be contacted by phone. Should the subject be interested in the study, they can call the study physician or coordinator to inquire about study participation. We will also recruit from our existing database of research participants.

Subjects who respond will be given a thorough review of the risks, discomforts, potential benefits to the study and their expected involvement using a prepared script approved by our Institutional Review Board. Subjects will be given a copy of the informed consent and allowed a minimum of 24 hours to review the information and make a decision on study participation. During this time, the subject will have the opportunity to discuss the research with his/her primary care physician or clinician. The study investigators will be available to answer any questions should any arise. Informed consent will be obtained by the Principal Investigator or an experienced co-investigator prior to participation in the study. The opportunity to talk to a licensed MD (who is readily available at the time of consent, and available overnight at the hospital) will be offered in each case. Subjects will have more than 24 hours to consider participating in the study. Any consent issues / problems will be reported to the PHRC in real time rather than waiting to report at the time of Continuing Review

Inclusion and exclusion criteria will be carefully assessed prior to enrollment. Assuming subjects meet the inclusion criteria, they will begin the protocol by scheduling their overnight studies in the clinical/physiology laboratories. Subjects will be informed that they may withdraw from the study at any point, with no impact on their ongoing care. We have not previously had difficulty enrolling participants into similar studies performed in our laboratory.

If the data collected will be considered insufficient by the PI or by the co-investigators, the subject will be asked to repeat the whole study or a part of it without signing a new informed consent form.

V. STUDY PROCEDURES

Protocol:

PARTNERS HUMAN RESEARCH COMMITTEE

DETAILED PROTOCOL

Version: March 8, 2017

Two overnight sleep studies will be performed approximately 1 week apart: a placebo night and a atomoxetine-plus-fesoterodine (DAW1033B2) night, in double-blinded randomized control design. For each night, the subjects will arrive at the sleep laboratory at approximately 7:00pm. A physician will perform a comprehensive physical and medical history. The placebo or atomoxetine-plus-fesoterodine (80+4mg) will be administered 30 minutes before lights out.

Measurements and equipment:

Subjects will be instrumented with standard polysomnography (PSG) recording sensors. Sleep stage and arousals will be measured with electrodes pasted on to the scalp, face, chin and chest (EEG, EOG, EKG, chin EMG). Paste-on EMG electrodes will be placed over the anterior tibialis muscle to detect leg movements. Respiratory effort belts will be placed around the chest and abdomen to measure breathing movements. Oxygen saturation will be measured continuously with a pulse oximetry probe placed on either the fingertip or earlobe. Snoring will be detected with a small microphone positioned over the suprasternal notch. Body position will be recorded with a sensor taped to the thoracic belt. Each of these devices is standard for diagnostic PSG and should not be uncomfortable.

Data analysis:

Apnea, hypopneas, sleep stages and arousals from sleep will be scored by a registered technician blinded to the treatment allocation. Hypopneas will be defined as a 30% reduction of the amplitude of the nasal pressure signal associated with an arousal from sleep or a 3% desaturation.

Reimbursement

Subjects will receive \$100/night for participation in each overnight study (TOTAL = \$200 for each PART of the study). Reimbursement for parking expenses will be provided.

If the subjects will repeat a part or the entire protocol because of insufficient data collection, they will be reimbursed \$100 for any extra night.

VI. BIostatistical ANALYSIS

Subjects will be prospectively enrolled until 12 had completed both study nights. Sample size was chosen to facilitate detection of a clinically-important 50±55% reduction in AHI. Calculations were based on previous studies conducted in our laboratory. To account for a ~20% failure rate approximately 15 patients will be enrolled in the study.

In order to reduce the influence of potential outlier, data will be expressed as median [interquartile range] and data on placebo vs DAW1033B2 will be compared using Wilcoxon test. A p value < 0.05 will be considered as statistically significant.

VII. RISKS AND DISCOMFORTS

We believe that the risks associated with participation in this study are minimal. All study procedures have been conducted in our laboratory without serious incident. Anticipated risks and discomforts are listed below:

1. The equipment used for assessing sleep (paste on electrodes) is standard and poses no risk. The electrodes may be mildly uncomfortable and could cause some sleep interruption. Thus subjects may feel somewhat tired the day following this study.

**PARTNERS HUMAN RESEARCH COMMITTEE
DETAILED PROTOCOL**

Version: March 8, 2017

2. Atomoxetine: Side effects include alopecia, dry mouth, tiredness, irritability, nausea, decreased appetite, constipation, dizziness, sweating, dysuria, sexual problems, decreased libido, urinary retention or hesitancy, increased obsessive behavior, weight changes, slowed growth in children, palpitations, increases in heart rate and blood pressure.
3. Fesoterodine: the most common side effects of fesoterodine 4 mg extended release in previous clinical trials were dry mouth and constipation. Less frequent side effects were abdominal pain, dry eyes, dyspepsia and urinary retention.

VIII. POTENTIAL BENEFITS

Although it is unlikely that there will be any direct physical benefit to the subjects from participating in this study, we will make known to each subject, if requested, some of the information we have gathered from this physiologic testing. This study provides a unique opportunity to gain insight into the specific mechanisms by which these novel drugs may improve upper airway muscle function. The results may, in the future, lead to improved strategies for the treatment of sleep apnea. However, if previously unknown abnormalities of sleep and breathing are encountered, this information will be passed onto the subject. Results can be forwarded to the primary care physician or clinician at the request of the subject.

IX. MONITORING AND QUALITY ASSURANCE

We will follow the Data and Safety Monitoring Plan included as an attachment. As this study is a physiological investigation and not clinical trial, a formal Data and Safety Monitoring Board will not be implemented. The PI will be responsible for monitoring safety and quality assurance. Additionally, the ongoing results, problems, and limitations of the study will be presented on a regular basis to the investigators in the Division of Sleep Medicine. Any adverse events will be promptly reported to the Human Research Committee for review according to HRC guidelines.

Adequacy of Protection Against Risks

All of our laboratory personnel involved in the research of human subjects have completed the required institutional program for education in the protection of human research participants and their confidentiality. The institutional educational program consists of the review of regulatory and informational documents pertaining to human-subject research, passing a test demonstrating knowledge of the ethical principles and regulations governing human-subject research and signing a statement of commitment to the protection of human subjects.

All electronic data will be stored on secure computers under password protection with no access allowed to individuals outside of our research team. All paper data will be stored under lock and key with access only given to the study staff.

Protection Against Risks

PARTNERS HUMAN RESEARCH COMMITTEE DETAILED PROTOCOL

Version: March 8, 2017

We believe that all possible safeguards are in place to minimize the risk. However, several steps will be taken to insure patient comfort and safety. We will work with our IRB to come up with a safety monitoring plan to minimize risk and discomfort. This will include:

- Reporting any complications of our studies immediately to the IRB.
- Appoint a safety officer ([name]) who will work with our physicians and technicians to maximize safety and comfort.
- Our study coordinator will call each subject 2-3 weeks after the study to determine if any problems resulted from the study.

The study coordinator will meet with the safety officer and PI monthly (and as needed) to go over any complaints or problems. The safety officer will call the patients with problems directly to verify important issues. If problems are identified, the protocol will be adjusted as needed. Based on conversations with the NIH and the NHLBI policy (<http://www.nhlbi.nih.gov/funding/ethics.htm>), we will not require a formal data safety monitoring board. However, we do have a thorough data safety monitoring plan whereby our safety officer will review all adverse events in order to classify them as serious adverse events, minor adverse events, and whether they are anticipated or unanticipated, and study related or unrelated as per our IRB rules and the NHLBI policy. The medical monitor will be an academic physician with considerable experience in clinical research but not involved in our research program or a co-investigator in any of our studies ([name]). The medical monitor will strictly adhere to the following definitions:

Definitions

Definitions are per January 2007 OHRP *Guidance on Reviewing and Reporting Unanticipated Problems Involving Risks to Subjects or Others and Adverse Events*, OHRP Guidance, <http://www.hhs.gov/ohrp/policy/AdvEvtGuid.htm>

Adverse Event (AE): any untoward or unfavorable medical occurrence in a human subject, including any abnormal sign (for example, abnormal physical exam or laboratory finding), symptom, or disease, temporally associated with the subject's participation in the research, whether or not considered related to the subject's participation in the research.

Serious adverse event (SAE): any adverse event that:

- Results in death
- Is life threatening, or places the subject at immediate risk of death from the event as it occurred
- Requires or prolongs hospitalization
- Causes persistent or significant disability or incapacity
- Results in congenital anomalies or birth defects
- Is another condition which investigators judge to represent significant hazards

Unanticipated Problem (UP): any incident, experience, or outcome that meets all of the following criteria:

- unexpected, in terms of nature, severity, or frequency, given the research procedures that are described in the protocol-related documents, such as the IRB-approved research protocol and informed consent document; and the characteristics of the subject population being studied;

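### The allergy exclusion names atomoxetine/oxybutynin, but the active night gives atomoxetine plus fesoterodine

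*Combined protocol and SAP*

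**What the plan says.** Section III lists the exclusions as bullets. One of them concerns allergy: "Allergy to lidocaine, Oxymetazoline HCl, desipramine, atomoxetine/oxybutynin, dalfampridine, pseudoephedrine HCl, diphenhydramine".

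The treatment is described in three other places. Section II (Specific Aims) sets out to test atomoxetine combined with fesoterodine, and it brings in oxybutynin only for comparison: "Fesoterodine is an extended-release antimuscarinic with less reported side effects compared to oxybutynin". Section V (Protocol) states what is given: "The placebo or atomoxetine-plus-fesoterodine (80+4mg) will be administered 30 minutes before lights out". Section VII (Risks and Discomforts) has one entry for atomoxetine and one for fesoterodine, the latter beginning "Fesoterodine: the most common side effects of fesoterodine 4 mg extended release in previous clinical trials were dry mouth and constipation". It has no oxybutynin entry.

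On how the criteria are used, Section IV (Subject Enrollment) says: "Inclusion and exclusion criteria will be carefully assessed prior to enrollment".

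**The concern.** An allergy exclusion in a drug study is there to keep out people known to react to what they will be given. Here the list has the wrong antimuscarinic. It names oxybutynin, which the study does not give, and leaves out fesoterodine, which it does.

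The written criteria are what staff check before enrolling someone. A volunteer with a known fesoterodine allergy could pass the allergy bullet as it stands, and whether any other bullet would stop that person is unclear. Each enrolled subject is due at least one active night. Section IV also lets the investigators ask for all or part of the study to be repeated without a new consent form, so some subjects may have more than one. This is a matter of eligibility and safety; it does not bear on the analysis.

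**Working it through.** The plan gives no figure to reproduce here. The check is a comparison of the text, with simple counts.

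**Step 1: the two antimuscarinics, section by section.**

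| Place | Atomoxetine | Fesoterodine | Oxybutynin |
|---|---|---|---|
| II, aim | study drug | study drug | comparison only |
| III, allergy bullet | named | absent | named |
| V, drug given | yes | yes | no |
| VII, drug risks | listed | listed | absent |

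The allergy bullet is the only row out of line. It names 1 of the 2 active drugs. This count takes the slash between atomoxetine and oxybutynin as separating two drugs. If it denotes the combination, even atomoxetine on its own is not clearly listed.

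**Step 2: can the oxybutynin entry stand for fesoterodine?** No. Section II sets the side effects of one against those of the other, so the protocol itself treats them as different drugs.

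**Step 3: does another exclusion fill the gap?** The bullets number 4 before the allergy bullet, plus 7 from the allergy bullet to the end of the list: 4 + 7 = 11. One concerns allergy and none names fesoterodine. Three others come near:

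- "Individuals taking psychiatric medications, such as Tricyclic antidepressants, or any of the studied medications for medical care" concerns people who take a drug. Someone allergic to fesoterodine is unlikely to be taking it.
- The bullet on prostatic hyperplasia and urinary retention mentions antimuscarinics, but it concerns those urinary conditions and not allergy.
- "Any medical condition other than well controlled hypertension, GERD, hyperlipidemia" could be stretched to a known drug allergy. But the protocol lists drug allergies by name in a bullet of their own, which suggests that the general bullet was not meant to do that work.

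**Step 4: do other steps catch such a person?** Sections IV and V describe four:

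1. a risk review, with the subject's "expected involvement using a prepared script approved by our Institutional Review Board";
2. at least 24 hours with the consent form and the chance to consult the subject's own clinician;
3. an offer to speak to a licensed physician;
4. a physician's history and examination on the study night.

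Any of these may reveal an allergy. None is described as an allergy check, and the fourth comes after enrollment.

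**Step 5: who is exposed.** Section VI plans for 12 completers and, allowing for a failure rate of about 20%, roughly 12 / 0.80 = 15 enrolled. At least 12 subjects therefore receive fesoterodine, and about 15 if everyone enrolled reaches the active night. The figure of 15 is an expectation, not a cap. These are numbers exposed to the drug, not numbers harmed by the omission.

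**Step 6: the rest of the list.** With the slash read as a separator, the bullet names eight agents. Only atomoxetine is given under any procedure described. The other seven are oxybutynin, lidocaine, oxymetazoline, desipramine, dalfampridine, pseudoephedrine and diphenhydramine. Section VI refers to study nights, and Section V's reimbursement text speaks of separate parts of the study, so the list may have been carried over from a wider protocol. That is an inference, and it would explain the mismatch without removing it.

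**The case against.** The best case for leaving the text alone is that little follows from it. A physician takes a history described as comprehensive on each study night, in a passage placed before the dosing statement, and such a history need not itemize allergy in order to cover it. Section III also requires subjects to be otherwise healthy and without active medical problems. The sample is small, the frequency of the allergy is not given, and no part of the statistical analysis changes. On this view it is a minor drafting slip.

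Much of that stands as an argument about size. The safeguards make harm less likely, and the number affected is probably small. It does not rescue the criterion. Neither the history nor the general health requirement names allergy, and the history comes after the point at which Section IV says eligibility is assessed. A stated eligibility rule that omits one of two study drugs should not depend on a later step to make it good.

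It is also fair to say that the mismatch is wider than fesoterodine, because most agents on the list are not given in this study. That is a reason to look at the whole bullet when it is amended.

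**Conclusion.** The concern holds. The allergy exclusion does not match the study treatment: it names 1 of the 2 active drugs, and 0 of the 11 exclusion bullets name fesoterodine. It should be fixed. The mismatch is certain on the text, while its practical effect is probably small and cannot be computed from the documents.

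The conclusion rests on the written criteria alone. The recruitment script, the consent form and the safety monitoring plan are not available here, so nothing is claimed about how subjects are screened in practice. The count of 1 in 2 assumes that the slash separates two drugs. The sample size, the Wilcoxon test and the error rate are not touched.

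**What to change.** Reconcile the allergy exclusion in Section III with the study combination as described in Sections II, V and VII. The same edit is the time for the investigator to confirm whether the other listed agents that no described procedure uses belong in this protocol. Then check that the recruitment script agrees with the reconciled criterion; the consent form is worth the same check. The wording of the criterion is for the investigator to settle.

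The cost is a one-line amendment and a document check. Because the script is approved by the review board, any change to it would presumably need that board's review. The plan for 12 completers and about 15 enrolled, and the analysis, stay as they are.

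### Section IX has ongoing results shown regularly to division investigators during a double-blind two-night study, without limiting them to masked or pooled data

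*Combined protocol and SAP*

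**What the plan says.** - **What is shown (section IX).** The protocol states that "the ongoing results, problems, and limitations of the study will be presented on a regular basis to the investigators in the Division of Sleep Medicine". Results are listed separately from problems and limitations, so the sentence cannot be read as covering safety or logistics only. The same section says that "a formal Data and Safety Monitoring Board will not be implemented", makes the PI responsible for safety and quality, and refers to an attached Data and Safety Monitoring Plan that is not among the supplied documents.
- **Blinding (section V).** Each subject has a placebo night and a drug night about one week apart, "in double-blinded randomized control design". The only role whose blinding is spelled out is the scorer: sleep and respiratory events "will be scored by a registered technician blinded to the treatment allocation".
- **Accrual (section VI).** "Subjects will be prospectively enrolled until 12 had completed both study nights". About 15 are to be enrolled to allow for failures of roughly 20%; failure is not defined.
- **Discretion over data (section IV).** "If the data collected will be considered insufficient by the PI or by the co-investigators", the subject is asked to repeat all or part of the study. No criterion for insufficiency is given.
- **Release to subjects (section VIII).** Some information is given to subjects on request, and results may go to their clinician.

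**The concern.** Ongoing results presented regularly during one-by-one accrual will reach investigators before the last subject is studied. In a parallel-group trial, uncoded individual results reveal little. Here the two nights of one subject sit side by side, one of them is known to be drug, and the plan expects the drug to halve AHI. A display of paired values therefore suggests both the allocation and the emerging effect.

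What is at stake is the set of nights that enters the analysis. The PI and co-investigators decide whether a recording is good enough to keep, and someone must decide whether a subject is a failure to be replaced. Neither decision has a written criterion. If those deciding have seen the AHI values, an unfavourable pair is easier to call insufficient than a favourable one. Blinded scoring does not guard against this, because the choice concerns which recordings count, not how events are scored.

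**Working it through.** **1. The plan's own figures.** Enrolment: 12/(1 − 0.20) = 15, as stated. For the completers, read 50±55% as mean and SD, so d = 50/55 = 0.909. With a two-sided 5% level and 80% power (both assumed; the plan states neither sidedness nor power), a paired t-test needs 12 subjects and has 81.7% power at 12. The stated number fits this reading of the ± sign. Simulated power of the Wilcoxon signed-rank test at 12 is about 77.7%.

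**2. How much an uncoded pair reveals.** Suppose the reader takes the lower-AHI night as the drug night. The guess is right when the reduction is above zero:

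P(reduction > 0) = Φ(50/55) = Φ(0.909) ≈ 0.82.

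That is about 12 × 0.82 ≈ 9.8 of 12 subjects, against 6 by coin toss. Normality is rough: it also puts 1 − Φ((100 − 50)/55) ≈ 18% of subjects above a 100% reduction, which is impossible. If 55% leaves out night-to-night variation, the figure would be lower.

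**3. How much one discretionary repeat can matter.** For 12 pairs without ties, the exact two-sided signed-rank p-value is 2 × (number of subsets of ranks 1 to 12 with sum ≤ W)/4096, where W is the smaller rank sum.

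| W | Subsets | p |
|---|---|---|
| 12 | 70 | 0.034 |
| 13 | 87 | 0.042 |
| 14 | 107 | 0.052 |
| 17 | 189 | 0.092 |

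The test is significant only if W ≤ 13. As a constructed example, let three subjects do worse on drug, with ranks 2, 5 and 10. Then W = 17 and p = 0.092. If the rank-5 subject is repeated and the new pair favours the drug at the same rank, W = 12 and p = 0.034. One repeat crosses the threshold. This shows sensitivity, not likelihood: the documents give no rate of repeats.

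**4. Whether the sections can be reconciled.** Section V sets a double blind. Section IX orders regular presentation of results and does not say in what form. The supplied text does not say who holds the code or when it is broken. The two sections are compatible only if the presentations leave out paired and by-treatment efficacy values, and no supplied sentence requires that.

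**The case against.** The strongest reply is that no unblinding is stated. Section IX does not say that results are shown by treatment, by paired night or with the code; the double-blind statement covers the whole study; and the attached monitoring plan may already restrict what is shown. This stands, so the fault is a missing limit on a stated rule, not a declared breach of the blind. A guess made after both nights also cannot change recordings already made, and scoring is blinded. That stands too, but it does not cover repeats and failure calls.

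A reader might infer more, and the documents do not support it:

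- **An inflated type I error.** If the results were tested at p < 0.05 at every look and the study stopped on success, simulation with no drug effect gives 4.2% for one look at 12, 7.8% for looks at 6, 9 and 12, and 10.9% for a look after every completer from 6 to 12. These are hypothetical. The plan has no interim test and no early stop, and 12 completers is a fixed count that does not depend on outcome.
- **False positives from selective enrolment.** "Informed consent will be obtained by the Principal Investigator or an experienced co-investigator prior to participation in the study", and overlap with the division audience is likely though not stated. But each subject is his or her own control. With no drug effect, choosing who enrols next cannot create a paired difference; it can affect generalisability.
- **Protocol changes driven by efficacy.** The sentence "If problems are identified, the protocol will be adjusted as needed" follows the meeting of coordinator, safety officer and PI about complaints and problems. It is a safety provision.

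**Conclusion.** The point holds as a cheap improvement. As supplied, section IX orders regular presentation of ongoing results during accrual and sets no limit that protects the blind claimed in section V. Paired AHI values would suggest allocation in about 82% of subjects, if 50±55% is a mean and SD with approximate normality. The route to bias is the undefined discretion over insufficient data, repeat nights and failures, exercised by people who may have seen those values. With 12 pairs, one such decision can move the result across 0.05. The likely size of the bias cannot be estimated from the documents, and no error rate above the nominal one can be assigned to the plan. The conclusion assumes that the unsupplied monitoring plan does not already restrict the presentations; if it does, section IX need only say so.

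**What to change.** 1. In section IX, replace the list of what is presented with: *enrolment, data completeness, operational problems, and adverse events pooled over both nights*.
2. Add: *No AHI or other efficacy result, by treatment or by paired night, is presented to investigators until both nights of the 12th completer are scored and locked. The safety officer and medical monitor may unblind for an individual event.*
3. In sections IV and VI, add that decisions on insufficient data, repeat nights and failures rest on recording quality alone and are made blind to AHI and allocation.
4. In section VIII, add that results requested by subjects or their clinicians are released after lock, except abnormal or safety findings.
5. If the attached monitoring plan already contains such limits, cite it in section IX.

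The cost is a few sentences across four sections. The division sees efficacy results, and subjects see their routine results, only at the end of a small study. Oversight of individual safety events is unchanged.
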